6.2.3. Sensitivity Analysis for Secondary Efficacy Endpoints

Sensitivity analyses of the secondary efficacy endpoints, the number of supplemental O₂-free days through Day 28, the proportion of subjects who develop respiratory failure requiring mechanical ventilation through Day 28, and the proportion of subjects with all-cause mortality through Day 28, will be performed in the PP analysis set.

6.3. Exploratory Efficacy Endpoints

6.3.1. Definition of Exploratory Efficacy Endpoints

PPD

[figure not shown]

6.3.2. Analysis Methods for Exploratory Efficacy Endpoints

PPD

[figure not shown]

PPD

PPD

6.4. Changes From Protocol-Specified Efficacy Analyses

- The number of supplemental O₂-free days through Day 28 will be analyzed using a negative binomial model with stratification factors as covariates. An offset parameter will be included to account for differential study durations.

7. SAFETY ANALYSES

7.1. Adverse Events and Deaths

7.1.1. Adverse Event Dictionary

Clinical and laboratory AEs will be coded using the current version of the Medical Dictionary for Regulatory Activities (MedDRA). System organ class (SOC), high level group term (HLGT), high level term (HLT), preferred term (PT), and lower level term (LLT) will be provided in the AE dataset.

7.1.2. Adverse Event Severity

Severity of adverse events will be determined by the investigator as Grade 1 (mild), Grade 2 (moderate), Grade 3 (severe), or Grade 4 (life-threatening). The severity of events for which the investigator did not record severity will be categorized as “missing” for tabular summaries and data listings. The missing category will be listed last in summary presentation.

7.1.3. Relationship of Adverse Events to Study Drug

Related AEs are those for which the investigator selected “Related” on the AE eCRF to the question of “Related to Study Treatment.” Relatedness will always default to the investigator’s choice, not that of the medical monitor. Events for which the investigator did not record relationships to study drug will be considered related to study drug for summary purposes. However, by-subject data listings will show the relationship as missing.

7.1.4. Serious Adverse Events

Serious adverse events will be identified and captured as SAEs if AEs met the definitions of SAEs that were specified in the study protocol. SAEs captured and stored in the clinical database will be reconciled with the SAE database from the Gilead Drug Safety and Public Health Department before database finalization.

7.1.5. Treatment-Emergent Adverse Events

7.1.5.1. Definition of Treatment-Emergent Adverse Events

Treatment-emergent adverse events (TEAE) are defined as 1 or both of the following:

- Any AEs with an onset date on or after the study drug start date up to the Day 28, or up to 28 days if a subject withdraws early (prior to Day 28) from the study
- Any AEs leading to premature discontinuation of study drug

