7.1.5.2. Incomplete Dates

If the onset date of the AE is incomplete and the AE stop date is not prior to the first dosing date of study drug, then the month and year (or year alone if month is not recorded) of onset determine whether an AE is treatment emergent. The event is considered treatment emergent if both of the following 2 criteria are met:

- The AE onset is the same as or after the month and year (or year) of the first dosing date of study drug, and
- The AE onset date is the same as or before the month and year (or year) of the Day 28

An AE with completely missing onset and stop dates, or with the onset date missing and a stop date later than the first dosing date of study drug, will be considered to be treatment emergent. In addition, an AE with the onset date missing and incomplete stop date with the same or later month and year (or year alone if month is not recorded) as the first dosing date of study drug will be considered treatment emergent.

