7.1.6. Summaries of Adverse Events and Deaths

Treatment-emergent (TE) AEs will be summarized based on the Safety Analysis Set.

The number and percentage of subjects who experienced at least 1 TEAE will be provided and summarized by SOC and PT, and treatment group. For other AEs described below, summaries will be provided by SOC, PT, and treatment group:

- TEAE by maximum severity
- TEAEs of Grade 3 or higher (by maximum severity)
- TEAEs of Grade 2 or higher
- All TE treatment-related AEs
- All TE treatment-related AEs by maximum severity
- TE treatment-related AEs of Grade 3 or higher (by maximum severity)
- TE treatment-related AEs of Grade 2 or higher
- All TE SAEs
- All TE treatment-related SAEs
- All TEAEs leading to premature discontinuation of study drug

- All TEAEs leading to premature discontinuation of study
- All AEs leading to death (ie, outcome of death)

A brief, high-level summary of AEs described above will be provided by treatment group and by the number and percentage of subjects who experienced the above AEs. All deaths observed in the study will be also included in this summary.

Multiple events will be counted only once per subject in each summary. Adverse events will be summarized and listed first in alphabetic order of SOC and HLT within each SOC (if applicable), and then by PT in descending order of total frequency within each SOC. For summaries by severity grade, the most severe grade will be used for those AEs that occurred more than once in an individual subject during the study.

In addition to the above summary tables, all TEAEs, TE treatment-related AEs, and TE SAE will be summarized by PT only, in descending order of total frequency.

In addition, data listings will be provided for the following:

- All AEs, indicating whether the event is treatment emergent
- All AEs of Grade 3 or higher
- All AEs of Grade 2 or higher
- SAEs
- Deaths
- All AEs leading to death (ie, outcome of death)
- AEs leading to premature discontinuation of study drug
- AEs leading to premature discontinuation of study

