7.2.2.1. Treatment-Emergent Laboratory Abnormalities

Treatment-emergent laboratory abnormalities are defined as values that increase at least 1 toxicity grade from baseline at any postbaseline time point, up to and including Day 28. If the relevant baseline laboratory value is missing, any abnormality of at least Grade 1 observed within the time frame specified above will be considered treatment emergent.

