15.11.2.3.3.3	Treatment-Emergent Treatment-Related Adverse Events with Severity of Grade 3 or Above by Preferred Term	Safety Analysis Set
15.11.2.3.3.4	Treatment-Emergent Treatment-Related Adverse Events with Severity of Grade 2 or Above by Preferred Term	Safety Analysis Set
15.11.2.4	Treatment-Emergent Adverse Events of Interest (Cardiac Adverse Event) by System Organ Class and Preferred Term	Safety Analysis Set
15.11.3	Treatment-Emergent Adverse Events Leading to Death by System Organ Class and Preferred Term	Safety Analysis Set
15.11.4.1	Treatment Emergent Serious Adverse Event by System Organ Class and Preferred Term	Safety Analysis Set
15.11.4.2	Treatment Emergent Serious Adverse Event by Preferred Term	Safety Analysis Set
15.11.4.3.1	Treatment Emergent Treatment-Related Serious Adverse Events by System Organ Class and Preferred Term	Safety Analysis Set
15.11.4.3.2	Treatment Emergent Treatment-Related Serious Adverse Events by Preferred Term	Safety Analysis Set
15.11.4.4	Treatment-Emergent Serious Adverse Events of Interest (Cardiac Adverse Event) by System Organ Class and Preferred Term	Safety Analysis Set
15.11.5.1	Treatment-Emergent Adverse Events Leading to Premature Discontinuation of Study Drug by System Organ Class and Preferred Term	Safety Analysis Set
15.11.5.2	Treatment-Emergent Adverse Events Leading to Premature Discontinuation of Study by System Organ Class and Preferred Term	Safety Analysis Set
15.11.6.1.1	Hematology Test: Hemoglobin (g/dL) and Change from Baseline	Safety Analysis Set
15.11.6.1.2	Hematology Test: Lymphocytes ($\times 10^3/\mu\text{L}$) and Change from Baseline	Safety Analysis Set

Table Number	Title	Analysis Set
15.11.6.1.3	Hematology Test: Lymphocytes (%) and Change from Baseline	Safety Analysis Set
15.11.6.1.4	Hematology Test: Monocytes ($\times 10^3/\mu\text{L}$) and Change from Baseline	Safety Analysis Set
15.11.6.1.5	Hematology Test: Monocytes (%) and Change from Baseline	Safety Analysis Set
15.11.6.1.6	Hematology Test: Neutrophils ($\times 10^3/\mu\text{L}$) and Change from Baseline	Safety Analysis Set
15.11.6.1.7	Hematology Test: Neutrophils (%) and Change from Baseline	Safety Analysis Set
15.11.6.1.8	Hematology Test: Platelets ($\times 10^3/\mu\text{L}$) and Change from Baseline	Safety Analysis Set
15.11.6.1.9	Hematology Test: Leukocytes ($\times 10^3/\mu\text{L}$) and Change from Baseline	Safety Analysis Set
15.11.6.2.1	Chemistry Test: ALT (U/L) and Change from Baseline	Safety Analysis Set

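### The treatment-emergent AE definition has no worsening criterion, so a pre-dose AE that worsens on study can drop out of the treatment-emergent summaries

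*SAP*

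**What the plan says.** SAP Section 7.1.5.1 opens with "Treatment-emergent adverse events (TEAE) are defined as 1 or both of the following" and then lists two criteria:

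- "Any AEs with an onset date on or after the study drug start date up to the Day 28", with a variant for subjects who withdraw before Day 28.
- "Any AEs leading to premature discontinuation of study drug", which carries no condition on onset date.

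Section 7.1.5.2 deals with incomplete dates. There the month and year "of onset determine whether an AE is treatment emergent", with the stop date also used. Severity plays no part.

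Section 7.1.6 builds the AE tables on this definition: "Treatment-emergent (TE) AEs will be summarized based on the Safety Analysis Set". Section 7.2.2.1 defines emergence differently for laboratory data: "Treatment-emergent laboratory abnormalities are defined as values that increase at least 1 toxicity grade from baseline at any postbaseline time point".

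Appendix 1 schedules AE collection at Screening (Day -2 to -1), without a footnote restricting what is collected at that visit.

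**The concern.** AEs are collected before the first dose, so the database can hold AE records with a pre-dose onset. Some of these may get worse after dosing, and deterioration on drug is what a treatment-emergent summary is meant to show. A definition with no worsening clause has no place for such an event unless the subject also stops study drug because of it.

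Safety and tolerability are part of a secondary objective (Section 1.1). Planned enrolment is about 60 subjects in two arms, so a single severe or serious event left out of an arm's count is a visible change in that arm's percentage. The primary efficacy analysis is not touched.

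**Working it through.** The SAP gives no figure on this point to reproduce, so the check is to apply the written rule to each way a pre-dose AE could reach the database.

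1. **Pre-dose onset, worsens, study drug stopped because of it.** Meets the second bullet of 7.1.5.1. Included.
2. **Pre-dose onset, worsening entered as a new AE dated after the first dose.** The new record meets the first bullet. Included.
3. **Partial onset date in the same month and year (or year) as the first dose, stop date not before the first dose.** Included under 7.1.5.2, even if the true onset was before dosing.
4. **Onset date completely missing, with the stop date missing or after the first dose.** Included under 7.1.5.2.
5. **Pre-dose onset with a full date, worsens or becomes serious on study, study drug not stopped for it, one record kept with its original onset date.** Meets neither bullet, and 7.1.5.2 does not apply. Excluded.

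Only case 5 is lost. An illustration: a Grade 1 AE with onset on Day -1 reaches Grade 3 on Day 10 and drug continues. It is not a TEAE. The same course with onset on Day 1 is a Grade 3 TEAE.

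**How far the second bullet helps.** Doses are given on Days 1, 5, 9, 13 and 17 (Section 1.2), while the TEAE window runs to Day 28. A subject who has taken the Day 17 dose has none left to discontinue. For such a subject a worsening in the last 28 − 17 = 11 days of the window (Days 18 to 28) has no route through that bullet.

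**Where a case 5 event is missing.** In 7.1.6, the summaries by maximum severity, Grade 2 or higher, Grade 3 or higher, treatment-related and serious events are all limited to TEAEs. Section 7.1.7 describes the cardiac summaries without that limit, but Tables 15.11.2.4 and 15.11.4.4 are titled as treatment-emergent.

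**Where it is still visible.** The listings in 7.1.6 of all AEs (with a treatment-emergent flag), Grade 2 or higher, Grade 3 or higher, and SAEs are not limited to TEAEs. All deaths enter the high-level summary. The text of 7.1.6 also asks for "All AEs leading to death (ie, outcome of death" without a treatment-emergent limit, although the matching Table 15.11.3 is titled "Treatment-Emergent Adverse Events Leading to Death by System Organ Class and Preferred Term". Text and title should be aligned.

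**The SAP's defaults elsewhere.** An AE with both dates missing counts as treatment-emergent (7.1.5.2), and missing relatedness counts as related (7.1.3). A documented on-study worsening under case 5 gets no comparable treatment.

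**The case against.** The strongest objection is that the loss depends on a recording convention that the SAP need not contain. If sites open a new AE when an existing one worsens, the first bullet captures it and nothing is missing. Such instructions commonly sit in the protocol or the eCRF guidelines, which are not shown. This stands, and it makes the effect conditional. It does not remove the point, because the definition of a TEAE is the SAP's own rule, and the SAP neither covers case 5 nor cites a convention that would prevent it.

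Other objections also limit the point. Section 5.3 collects disease-specific conditions as medical history, so having RSV infection at entry does not by itself create pre-dose AE records. Respiratory deterioration is measured directly by the secondary endpoints (oxygen-free days, respiratory failure, mortality), and laboratory, ECG and troponin changes have their own summaries. Both suggest that few events are affected.

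Four stronger readings are tempting but not supported:

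- *The rule looks at onset date alone.* It does not; the discontinuation bullet ignores onset.
- *The AE and laboratory definitions contradict each other.* Laboratory values are serial measurements with a baseline and no onset date, so emergence has to be defined by change. AEs are dated records. This is a contrast, not a contradiction.
- *A worsened pre-dose AE can appear only in listings.* Deaths are counted whatever the AE's status, and the text bullet on fatal AEs is not limited to TEAEs.
- *A number of missed events can be given.* That needs AE rates and worsening shares that the documents do not supply.

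**Conclusion.** The point holds in a limited form. As written, the definition omits one class of event: onset before the first dose, worse or serious on study, no discontinuation of study drug because of it, and a single record under the original onset date. Those events are left out of the treatment-emergent severity, relatedness and SAE summaries and the cardiac tables as titled, but stay in the listings.

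The size cannot be estimated from the documents. It is zero if each worsening is a new AE with a new onset date, and probably small otherwise. The same rule applies in both arms, so nothing here shows that the comparison is tilted towards either one. The conclusion assumes that at least some pre-dose conditions are recorded as AEs at Screening and that worsening may remain on the original record; the SAP does not rule out either.

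**What to change.** Before unblinding, add a third bullet to 7.1.5.1 to this effect: an AE that began before the first dose and that, between the first dose and Day 28, rises in severity grade or becomes serious. Tabulate it at its worst on-treatment grade. If the date of worsening is unknown and the AE continued past the first dose, treat the worsening as on-treatment, in line with the conservative handling of missing dates in 7.1.5.2.

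If the eCRF already records each worsening as a new AE with a new onset date, the bullet changes nothing, and a sentence in 7.1.5.1 citing that convention is enough. Section 7.7 shows that enrolment had already closed, so the convention in use can be confirmed from the eCRF instructions.

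The cost is one bullet and a modest change to the treatment-emergent flag. TEAE counts may rise slightly in both arms. The SAP does not show whether dated grade changes within a record are collected; if they are not, some records will need a query or will be classified by the conservative default.

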7.1.5.2. Incomplete Dates

If the onset date of the AE is incomplete and the AE stop date is not prior to the first dosing date of study drug, then the month and year (or year alone if month is not recorded) of onset determine whether an AE is treatment emergent. The event is considered treatment emergent if both of the following 2 criteria are met:

- The AE onset is the same as or after the month and year (or year) of the first dosing date of study drug, and
- The AE onset date is the same as or before the month and year (or year) of the Day 28

An AE with completely missing onset and stop dates, or with the onset date missing and a stop date later than the first dosing date of study drug, will be considered to be treatment emergent. In addition, an AE with the onset date missing and incomplete stop date with the same or later month and year (or year alone if month is not recorded) as the first dosing date of study drug will be considered treatment emergent.

7.1.6. Summaries of Adverse Events and Deaths

Treatment-emergent (TE) AEs will be summarized based on the Safety Analysis Set.

The number and percentage of subjects who experienced at least 1 TEAE will be provided and summarized by SOC and PT, and treatment group. For other AEs described below, summaries will be provided by SOC, PT, and treatment group:

- TEAE by maximum severity
- TEAEs of Grade 3 or higher (by maximum severity)
- TEAEs of Grade 2 or higher
- All TE treatment-related AEs
- All TE treatment-related AEs by maximum severity
- TE treatment-related AEs of Grade 3 or higher (by maximum severity)
- TE treatment-related AEs of Grade 2 or higher
- All TE SAEs
- All TE treatment-related SAEs
- All TEAEs leading to premature discontinuation of study drug

- All TEAEs leading to premature discontinuation of study
- All AEs leading to death (ie, outcome of death)

A brief, high-level summary of AEs described above will be provided by treatment group and by the number and percentage of subjects who experienced the above AEs. All deaths observed in the study will be also included in this summary.

Multiple events will be counted only once per subject in each summary. Adverse events will be summarized and listed first in alphabetic order of SOC and HLT within each SOC (if applicable), and then by PT in descending order of total frequency within each SOC. For summaries by severity grade, the most severe grade will be used for those AEs that occurred more than once in an individual subject during the study.

In addition to the above summary tables, all TEAEs, TE treatment-related AEs, and TE SAE will be summarized by PT only, in descending order of total frequency.

In addition, data listings will be provided for the following:

- All AEs, indicating whether the event is treatment emergent
- All AEs of Grade 3 or higher
- All AEs of Grade 2 or higher
- SAEs
- Deaths
- All AEs leading to death (ie, outcome of death)
- AEs leading to premature discontinuation of study drug
- AEs leading to premature discontinuation of study

7.1.7. Additional Analysis of Adverse Events

Summaries (number and percentage) of subjects who experienced any cardiac related events will be provided for each treatment group using the Safety Analysis Set by AE of interest categories and the associated PTs (see Appendix 2).

7.2. Laboratory Evaluations

Laboratory data collected during the study will be analyzed and summarized using both quantitative and qualitative methods. Summaries of laboratory data will be provided for the Safety Analysis Set and will include data collected up to Day 28. The analysis will be based on values reported in conventional units. When values are below the LOQ, they will be listed as

such, and the closest imputed value will be used for the purpose of calculating summary statistics as specified in Section 3.7. Hemolized test results will not be included in the analysis, but they will be listed in by-subject laboratory listings.

A by-subject listing for laboratory test results will be provided by subject ID number and visit in chronological order for hematology and serum chemistry separately. Values falling outside of the relevant reference range and/or having a severity grade of 1 or higher on the Gilead Grading Scale for Severity of Adverse Events and Laboratory Abnormalities will be flagged in the data listings, as appropriate.

No formal testing will be generated.

7.2.1. Summaries of Numeric Laboratory Results

Descriptive statistics will be provided by treatment group for each laboratory test specified in the study protocol as follows:

- Baseline values
- Values at each postbaseline visit
- Change from baseline at each postbaseline visit

A baseline laboratory value will be defined as the last measurement obtained on or prior to the date/time of first dose of study drug. Change from baseline to a postbaseline visit will be defined as the visit value minus the baseline value. The mean, median, Q1, Q3, minimum, and maximum will be displayed to the reported number of digits; SD values will be displayed to the reported number of digits plus 1.

Median (Q1, Q3) of the observed values for the laboratory tests will be plotted using a line plot by treatment group and visit.

In the case of multiple values in an analysis visit, data will be selected for analysis as described in Section 3.8.3.

7.2.2. Graded Laboratory Values

The Gilead Grading Scale for Severity of Adverse Events and Laboratory Abnormalities will be used for assigning toxicity grades (0 to 4) to laboratory results for analysis. Grade 0 includes all values that do not meet the criteria for an abnormality of at least Grade 1. For laboratory tests with criteria for both increased and decreased levels, analyses for each direction (ie, increased, decreased) will be presented separately.

7.2.2.1. Treatment-Emergent Laboratory Abnormalities

Treatment-emergent laboratory abnormalities are defined as values that increase at least 1 toxicity grade from baseline at any postbaseline time point, up to and including Day 28. If the relevant baseline laboratory value is missing, any abnormality of at least Grade 1 observed within the time frame specified above will be considered treatment emergent.

7.2.2.2. Treatment-Emergent Marked Laboratory Abnormalities

Treatment-emergent marked laboratory abnormalities are defined as values that increase from baseline by at least 3 toxicity grades at any postbaseline time point, up to and including Day 28. If the relevant baseline laboratory value is missing, then any Grade 3 or 4 values observed within the timeframe specified above will be considered treatment-emergent marked abnormalities.

7.2.2.3. Summaries of Laboratory Abnormalities

Laboratory data that are categorical will be summarized using the number and percentage of subjects in the study with the given response at baseline and each scheduled postbaseline visit.

The following summaries (number and percentage of subjects) for treatment-emergent laboratory abnormalities will be provided by treatment group; subjects will be categorized according to the most severe postbaseline abnormality grade for a given lab test:

- Graded laboratory abnormalities
- Grade 3 or 4 laboratory abnormalities
- Marked laboratory abnormalities

For all summaries of laboratory abnormalities, the denominator is the number of subjects with nonmissing postbaseline values up to and including Day 28.

A by-subject listing of treatment-emergent Grade 3 or 4 laboratory abnormalities and marked laboratory abnormalities will be provided by subject ID number and visit in chronological order. This listing will include all test results that were collected throughout the study for the lab test of interest, with all applicable severity grades displayed.

